### **10.4 Causality Assessment**

The following “binary” decision choice will be used by the Investigator to describe the causality assessment:

- Reasonable possibility of a relatedness
- No reasonable possibility of relatedness

The expression “reasonable possibility of relatedness” is meant to convey, in general, that there are facts (evidence) or arguments meant to suggest a causal relationship.

The Investigator will be asked to consider the following before reaching a decision on causality assessment:

- Time relationship between study drug intake and event’s onset;
- Dechallenge (did the event abate after stopping drug?);
- Rechallenge (did the event reappear after reintroduction?);
- Medical history;
- Study treatment(s);
- Mechanism of action of the study drug;
- Class effects;
- Other treatments-concomitant or previous;
- Withdrawal of study treatment(s);
- Lack of efficacy/worsening of existing condition;
- Erroneous treatment with study medication (or concomitant);
- Protocol related process.

### **10.5 Action taken with the study drug due to an AE**

- Dose not changed
- Drug permanently withdrawn
- Drug temporarily interrupted
- Unknown
- Not applicable

Clinical Study Code: CLI-06001AA1-02	Version No.: 1.0
EUDRACT No.: 2020-004201-31	Date: 19 October 2020

### **10.6 Other actions taken**

- Specific therapy/Medication
- Concomitant Procedure

### **10.7 Outcome**

Each Adverse Event must be rated by choosing among:

- Recovered/resolved
- Recovering/resolving
- Not recovered/not resolved
- Recovered with sequelae/resolved with sequelae
- Fatal
- Unknown

### **10.8 Recording Adverse Events**

All Adverse Events occurring during the course of the study must be documented in the Adverse Event page of the electronic Case Report Form (eCRF). Moreover, if the Adverse Event is serious, the Serious Adverse Event Form must also be completed.

It is responsibility of the Investigator to collect all adverse events (both serious and non-serious) derived by spontaneous, unsolicited reports of subjects, by observation and by routine open questionings.

The recording period for Adverse Events is the period starting from the Informed Consent signature until the subject's study participation ends.

Clinically significant abnormalities detected at Screening not due to a pre-existing condition or clinically significant changes at the following visits in the medical opinion of the investigator must be reported as adverse events in the eCRF.

If a clinically significant abnormal laboratory finding or other abnormal assessment meets the definition of an AE, then the AE eCRF page must be completed, as appropriate. A diagnosis, if known, or clinical signs and symptoms if diagnosis is unknown, rather than the clinically significant abnormal laboratory finding, should be reported on AE eCRF page. If no diagnosis is known and clinical signs and symptoms are not present, then the abnormal finding should be recorded.

For pharmacovigilance purposes, all SAEs should be followed-up in order to elucidate as completely and practically as possible their nature and/or causality until resolution of all queries, clinical recovery is complete, laboratory results have returned to normal, stable condition is reached or until the subject is lost to follow-up. Follow-up may therefore continue after the subject has left the study. In this case, the follow-up will continue with no timelines for related SAEs, while for unrelated SAEs the type and extent of follow-up undertaken will be determined for each individual case and will depend upon the nature (e.g. events with poor prognosis or which do not resolve), severity and medical significance of the event.

### **10.9 Reporting Serious Adverse Events to Chiesi**

The Investigator must report all Serious Adverse Events to the [REDACTED] Safety Contact listed below within 24 hours of awareness. The information must be sent by providing the completed paper Serious Adverse Event form. At a later date, the [REDACTED] Safety Contact will report all information to Chiesi Global Pharmacovigilance, the Clinical Project Manager and the Clinical Research Physician.

Clinical Study Code: CLI-06001AA1-02	Version No.: 1.0
EUDRACT No.: 2020-004201-31	Date: 19 October 2020

Name and Title	Telephone no.	Fax no.	E-mail
████████ Safety Contact	Not applicable	████████	████████
Chiesi Safety Contact ████████	████████	████████	████████

- Reporting of SAEs from the investigator site is from the time of subject's signature of informed consent and until the subject's study participation ends. After this date, even if no active monitoring of subjects is required, SAEs occurring to a subject should be reported if the investigator becomes aware of them.
- Up to the closure of the site, SAE reports should be reported to the █████ Safety Contact. New serious adverse events occurring after the site is closed should be reported directly to the Chiesi Safety Contact.

#### **10.10 Reporting Serious Adverse Events to Regulatory Authorities/Ethics Committees/IRB**

All SUSARs, which occur with the investigational medicinal products within or outside the concerned clinical trial, if required, will be reported in compliance with the timelines and standards for reporting SUSARs set out in the EU Directive 2001/20/EC [Directive 2001/20/EC of the European parliament and of the council of 4/April/2001] and linked guidance [European Commission, Enterprise and Industry Directorate General: Detailed guidance on the collection, verification and presentation of adverse event/reaction reports arising from clinical trials on medicinal products for human use, latest version]. The EMA and the concerned national health authority (if applicable) will be informed through Eudravigilance, or according to local requirements (as applicable) while the Ethics Committees and the investigators by CIOMS I form or by periodic line- listings produced by Chiesi Global Pharmacovigilance.

With regard to regulations in force for Pharmacovigilance, the Investigator must fulfill his/her obligation according to the law in force in his country.

#### **10.11 General Notes**

- In case of death, a comprehensive narrative report of the case should be prepared by the Investigator and sent to the █████ Safety Contact together with the Serious Adverse Event form, retaining a copy on site.
- If an autopsy is performed, copy of autopsy report should be actively sought by the Investigator and sent to the █████ Safety Contact as soon as available, retaining a copy on site.
- All documents provided by the Investigator or site staff to the █████ Safety Contact must be carefully checked for respect of confidentiality. All personal subject's data must be redacted.
- All source documents provided by the Investigator or site staff to the █████ Safety Contact must be carefully checked for respect of confidentiality. All personal subjects' data must be redacted.
- In case of pregnancy occurred to the subject's partner, the subject participating to the study should not be discontinued from the study. The pregnancy will be followed with due diligence until the outcome is known and till the age of one year to detect any congenital anomaly or birth defect.

The pregnancy must be reported by the investigator within 24 hours by fax/e-mail/via Monitor to the █████ Safety Contact using the paper Pregnancy Report Form. The █████ Safety Contact will inform Chiesi of the pregnancy within one working day of being notified.

Clinical Study Code: CLI-06001AA1-02	Version No.: 1.0
EUDRACT No.: 2020-004201-31	Date: 19 October 2020

The first two pages of the Pregnancy Report Form should be completed by the investigator with all the available information and sent to the [REDACTED] Safety Contact. The third page will be completed as soon as the investigator has knowledge of the pregnancy outcome, together with a follow-up of the first two pages, if necessary (e.g. an update in the medications received during pregnancy by the mother). If it meets the criteria for immediate classification of a SAE (e.g. spontaneous or therapeutic abortion, stillbirth, neonatal death, congenital anomaly, birth defect) the Investigator should follow the procedure for reporting SAEs.

- Any Adverse Drug Reaction (ADR) occurring with any marketed non-investigational medicinal product and/or concomitant medication during the study must be reported by the Investigator to his/her concerned Health Authority according to the applicable laws. The Investigator is also recommended to report all adverse drug reactions to the relevant Marketing Authorisation Holders of the involved medicinal products. Additionally, also conditions of use outside the marketing authorisation of the medicinal products (i.e. off-label, overdose, misuse, abuse and medication errors) or from occupational exposure, as well as cases of suspected drug interaction, pregnancy, breast-feeding exposure and lack of efficacy should be reported.

## 11. DATA MANAGEMENT

An electronic CRF (eCRF) will be filled-in by the Investigator and/or his/her representative designee. Front-end edit checks will run at the time of data collection and back-end edit checks will be used by the Data Manager to check for discrepancies and to ensure consistency and completeness of the data. Medical history, adverse events and concomitant procedures will be coded using the MedDRA dictionary; medications will be coded using the WHO Drug dictionary and Anatomical Therapeutic Chemical classification (ATC) up to level 5.

External data (PK concentrations) will be processed centrally, sent to the designated CRO and reconciled with the corresponding information recorded in the CRF as part of cleaning activities.

Access to electronic systems used for data collection will be granted to the study personnel only after appropriate training.

After the completion of data collection and cleaning, a review meeting will be held to determine the occurrence of any protocol violation and to define the subject populations for the analysis. Once the database has been declared to be complete and accurate, it will be locked, and the planned statistical analysis will be performed.

If the database is unlocked after the initial lock, the process must be carefully controlled and documented; updates to the study data must be authorized by Chiesi.

At the study conclusion, a complete copy of the study data will be created for archival purposes at Chiesi. The investigators will receive copies of the subject data for retention at the investigational sites.

## 12. STATISTICAL METHODS

### 12.1 Sample Size

According to the exploratory nature of the study, no formal sample size calculation was performed. A total of 8 subjects will be included in the study to characterize the absolute bioavailability and the mass balance of CHF6001.

Clinical Study Code: CLI-06001AA1-02	Version No.: 1.0
EUDRACT No.: 2020-004201-31	Date: 19 October 2020

## **12.2 Populations for analysis**

- Safety population: **all enrolled subjects who start study treatment inhalation.**
- **PK population:** all subjects from the safety population excluding subjects without any valid PK measurement or with major protocol deviations significantly affecting PK, for example: incorrect inhalation, change in subject condition (cold), failure in delivery of the device, use of non-permitted medications. Exact definition of major protocol deviations concerning PK will be discussed by the clinical team and described in a specific document before bioanalytical data are disclosed. Subjects will not be excluded on the basis of statistical analysis or for pharmacokinetic reasons, except in the cases defined in the EMA "Guideline on the Investigation of Bioequivalence" [21].

PK variables will be analysed in the PK population. The Safety population will be used in the analysis of all safety variables.

## **12.3 Statistical analysis**

A detailed statistical analysis plan will be described in the Statistical Analysis Plan. The plan might be reviewed and updated as a result of the review of the data and will be finalized before locking the database.

### **12.3.1 Descriptive Statistics**

All PK variables (except for  $t_{max}$ ,  $t_{max\_inh}$  and  $t_{max\_iv}$ ) will be summarized by means of descriptive statistics including n (number of observed values), arithmetic mean, standard deviation (SD), coefficient of variation (CV), geometric mean, geometric CV, median, minimum and maximum.  $t_{max}$ ,  $t_{max\_inh}$ ,  $t_{max\_iv}$  will be summarized by using n, median, minimum and maximum.

General descriptive statistics for other continuous variables will include the n (number of observed values), the mean, the standard deviation, the median, the minimum, and the maximum values.

For categorical variables, the number and percent of subjects with a specific level of the variable will be presented.

### **12.3.2 Missing data**

Details on dealing with missing data, along with the handling of possible outliers, will be described in the SAP.

### **12.3.3 Subject demographics and baseline characteristics**

Demographics and baseline variables will be summarized using descriptive statistics for the Safety population and PK (if different from safety population).

### **12.3.4 PK variables**

The following PK variables will be summarized by means of descriptive statistics as described in Section 12.3.1:

- Plasma [ $^{14}\text{C}$ ]-CHF6001,  $\text{AUC}_{0-t\text{ iv}}$ ,  $\text{C}_{max\_iv}$ ,  $t_{max\_iv}$ ,  $\text{AUC}_{0-\infty\text{ iv}}$ ,  $t_{1/2\text{ iv}}$ ,  $\text{V}_z$ ,  $\text{V}_{dss}$  and CL
- Plasma [ $^{14}\text{C}$ ]-total  $\text{AUC}_{0-t\text{ iv}}$ ,  $\text{C}_{max\_iv}$ ,  $t_{max\_iv}$ ,  $\text{AUC}_{0-\infty\text{ iv}}$ ,  $t_{1/2\text{ iv}}$
- Plasma CHF6001  $\text{AUC}_{(0-t)\text{ inh}}$ ,  $\text{C}_{max\_inh}$ ,  $t_{max\_inh}$ ,  $\text{AUC}_{(0-\infty)\text{ inh}}$ ,  $t_{1/2\text{ inh}}$ ,  $\text{F}_{inh}$

Clinical Study Code: CLI-06001AA1-02	Version No.: 1.0
EUDRACT No.: 2020-004201-31	Date: 19 October 2020

- Urine and feces [C]-CHF6001 and [C]-total excreted fraction (Feu, Fef and Feu+f)
- [C]-CHF6001 CLblood, CLR and CLR\_blood
- Blood to plasma ratio (Rb/p) [C]-CHF6001
- Blood to plasma ratio (Rbt/pt) [C]-total
- Femet
- Metabolites Frplasma, Frurine, Frfeces, Frurine+feces
- [C]-CHF6001 Eh\_blood

Concentration (mass equivalent in mL or mass in mL)/time curves for plasma total [C], [C]-CHF6001 and non-radiolabeled CHF6001 will be presented in linear/linear and log/linear scale. Plots will be presented based on arithmetic means and by subject (all individual plasma concentration/time curves in one graph).

Bar charts based on arithmetic means showing the percentage of urine and feces excreted fraction for total [C] and [C]-CHF6001 in the different time intervals will be presented.

Bar charts based on arithmetic means showing percentages of the relevant metabolites recovered in plasma, urine and feces will be presented.

All individual concentration data (mass equivalent per mL or mass per mL) and PK parameters will be listed. In addition, a listing of the actual sampling times relative to drug inhalation will be provided. Concentrations will be summarized by scheduled sampling time by using n, arithmetic mean, SD, CV, median, minimum and maximum.

### 12.3.5 Safety variables

#### Adverse Events

All adverse events starting on or after the time of first study drug inhalation will be classified as treatment emergent adverse event (TEAE). Any adverse events started after the informed consent signature and before the time of first study drug inhalation will be classified as pre-treatment adverse event.

The number of subjects who experienced at least one TEAE, drug-related TEAE, serious TEAE and TEAE leading to study discontinuation will be summarized. Summaries will be presented overall (number and percentage of subjects having at least one event, total number of events) and by system organ class and preferred term (number and percentage of subjects having at least one occurrence of that event).

All adverse events will be listed.

Pre-treatment adverse event will be listed only.

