## 7.1.2 Treatment Period

The subject will arrive at the clinical site on Day -1 and will stay overnight until the accomplishment of the 240 hours post-dose (i.v.) study procedures. All subjects will be discharged on Day 11.

Clinical Study Code: CLI-06001AA1-02	Version No.: 1.0
EUDRACT No.: 2020-004201-31	Date: 19 October 2020

- On Day -1, subjects will be hospitalised and will undergo the planned assessments and checks to confirm eligibility)
- On Day 1 of treatment period, subjects will undergo pre-dose assessments, then will receive the treatment and will start post-dose assessments.
- From Day 2 until Day 11, subjects will continue the post-dose assessments. Subjects will be instructed to continue to follow study restrictions (see section [7.1.4](#)). They will then be discharged soon after the 240h post-dose (i.v.) assessment.

The following procedures and assessments will take place during this period:

- SUBJECT TRAINING with devices: subjects will be trained on a proper use of the inhaler with In-Check Dial (Day -1/Day 1) and with the DPI placebo training kit (Day -1 and Day 1 pre-dose)
- SUBJECT SELECTION (Day -1): Inclusion criterion 6 and Exclusion criteria 7, 8, 9, 10, 11, 12 and 20, will be re-checked as requested in section [4.2](#) and [4.3](#). Subjects not fulfilling the mentioned criteria will be Screen Failed
- ALCOHOL BREATH TEST (Day -1): will be performed
- PHYSICAL EXAMINATION (Day 1): a full physical examination will be performed and any new revealed clinically significant abnormality since the screening visit will be recorded as an AE. Furthermore, a full physical examination will be performed at discharge.
- ADVERSE EVENTS RECORDING (Day -1 to Day 11): Any new AE/SAE occurred since the screening visit will be checked and recorded in the eCRF. The status of ongoing AEs will be checked and updated in the eCRF when applicable. Moreover, during this period in case of any new clinically significant abnormality revealed during the examination or procedures, it will be recorded as an adverse event.
- STUDY RESTRICTIONS (Day -1 to Day 11): study restrictions criteria will be checked.
- CONCOMITANT MEDICATIONS CHECK (Day -1 to Day 11): concomitant medications taken by the subject in the last 14 days and during the treatment period will be checked and recorded in the eCRF.

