10.2 Adverse Events

An AE will be classified as pre-treatment AE if it starts after the informed consent signature and before the time of first inhalation of the study drug (date of informed consent < AE onset date and AE onset date-time < date-time of first study drug inhalation).

All adverse events starting on or after the time of first study drug inhalation will be classified as treatment emergent adverse event (TEAE) (date-time of first study drug inhalation \leq AE onset date-time \leq date of discharge).

An AE will be classified as a post-study AE if it starts after the date of discharge (AE onset date $>$ date of discharge).

An adverse drug reaction (ADR) is an AE judged as related to the study medication.

A serious ADR is a serious AE (SAE) judged as related to the study medication.

A severe AE is an AE with severe intensity.

An AE leading to discontinuation will be identified based on the information collected in study termination form (i.e. reason for discontinuation =Adverse event).

An AE leading to death is an AE with outcome equal to “Fatal”.

Pre-treatment AEs, TEAEs and post-study AEs will be presented separately. Pre-treatment AEs and post-study AEs will be presented in the listings only.

The number of TEAEs, drug-related TEAE, serious TEAE and TEAE leading to study discontinuation and the number and the percentage of subjects experiencing TEAEs, drug-related TEAEs, serious TEAEs and TEAEs leading to study discontinuation will be summarised.

The MedDRA SOC and PT will also be used for tabulation. The number and percentage of subjects with at least one AE and the number of AEs will be presented by SOC and PT for the above categories of AEs.

Derived variables presented in the listings:

The relative day of AE onset will be calculated as follows:

- for pre-treatment AEs:
 - AE onset date - date of first inhalation of study drug (if AE onset date is completely known);
 - missing (if AE onset date is incomplete or unknown).
- For TEAEs and post-Study AEs:
 - AE onset date – date-time of first inhalation of study drug +1 (if AE onset date is completely known);
 - missing (if AE onset date is incomplete or unknown).

The duration of an AE (hours) will be calculated as follows:

- $(AE\ end\ date-time - AE\ onset\ date-time) / 3600$ (when both date-time are completely known)

The duration of an AE (days) will be calculated as follows:

If duration in hours ≥ 24 hours:

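### The TEAE definition rests on onset time alone, and the documents do not clearly say how a pre-dose AE that worsens after dosing is to be recorded, so it can be missing from the TEAE summaries

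*Protocol*

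**What the plan says.** Protocol 12.3.5 sets two classes by onset. The treatment-emergent class is: "All adverse events starting on or after the time of first study drug inhalation will be classified as treatment emergent adverse event (TEAE"). An event that "started after the informed consent signature and before the time of first study drug inhalation will be classified as pre-treatment adverse event". SAP 10.2 repeats the split: "An AE will be classified as pre-treatment AE if it starts after the informed consent signature and before the time of first inhalation" of study drug. The SAP adds a cut-off at discharge, which does not bear on this point.

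The summaries follow the first class. Protocol 12.3.5: "The number of subjects who experienced at least one TEAE, drug-related TEAE, serious TEAE and TEAE leading to study discontinuation will be summarized". For the other class it says: "Pre-treatment adverse event will be listed only". The SAP agrees: "Pre-treatment AEs and post-study AEs will be presented in the listings only".

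Two passages govern recording. On events still open during the residential period, protocol 7.1.2 says: "The status of ongoing AEs will be checked and updated in the eCRF when applicable". Protocol 10.8 adds that "clinically significant changes at the following visits in the medical opinion of the investigator must be reported as adverse events in the eCRF".

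**The concern.** AE recording starts at consent (protocol 10.8), and screening falls 3 to 31 days before dosing (protocol 7.1.1). A minor complaint can therefore be on record and unresolved when the subject inhales. If CHF6001 aggravates it, the drug effect shows as a change in an existing event, and an onset-only rule does not see that change.

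Safety and tolerability is one of the four stated objectives, and protocol 1.1 describes gastrointestinal effects as a known effect of the PDE4 inhibitor class. A post-dose aggravation left out of the tables makes the drug look better tolerated. The omission cannot work the other way, because the rule never adds an event to the TEAE class.

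**Working it through.** The plan has no figure to reproduce. There is no formal sample size calculation (protocol 12.1), no AE rate, and no testing or confidence intervals (SAP 7.1). The check is therefore a reading of the rules, plus the weight of one subject.

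**Inputs**
- Class rule: onset compared with the time of first inhalation (protocol 12.3.5, SAP 10.2).
- Output rule: the AE tables described in the text cover TEAEs; pre-treatment AEs are listed (same sections).
- Planned subjects: 8 (protocol 12.1, SAP 5).

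**Hypothetical case.** A mild complaint starts on Day -1, is unresolved at inhalation, and becomes moderate or serious afterwards. The outcome depends on how the site records it.

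| Recording by the site | Onset used by the rule | Class | Where it appears | Row, if no other event |
|---|---|---|---|---|
| Existing record updated | Before inhalation | Pre-treatment | Listing only | 0/8 = 0% |
| New entry for the worsening | After inhalation | TEAE | Tables and listing | 1/8 = 12.5% |

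Difference: 1/8 − 0/8 = 0.125, or 12.5 percentage points. If n subjects are dosed instead of 8, the difference is 1/n.

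The same shift applies to the overall TEAE row, to the drug-related row if the event is judged related, and to the serious row if it becomes serious.

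**Does any passage settle which line of the table applies?**
- Protocol 7.1.2 speaks of updating the status of ongoing AEs and recording new ones. It does not say whether a worsening counts as an update or as new.
- Protocol 10.8 could cover a worsening, but it does not say that an AE already recorded receives a second entry and a second onset.
- Protocol 10.3 asks for an intensity rating for each AE and gives no instruction for an intensity that changes.
- SAP 7.3.1 allocates doubtful AEs to the treatment-emergent class first, but only where dates or times are missing or incomplete. Here the onset is known.
- SAP 12 declares no change from the protocol analysis, so the SAP does not add a worsening rule.

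None of these brings a post-dose worsening into the TEAE class, and none clearly fixes the recording convention.

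**The case against.** The strongest reply is that the gap lies in recording and may already be closed. Protocol 7.1.2 mentions only status, which can be read as the outcome categories of protocol 10.7, and it does not forbid a new record. Protocol 10.8 contains no exclusion for AEs already recorded. Protocol 10.1 treats hospitalisation for a pre-existing condition differently when that condition has not worsened, and protocol 10.4 lists worsening of an existing condition among the causality considerations. The authors were therefore aware of worsening. The SAP cites a final eCRF, which was not available for this review and may carry the convention. If sites open a new entry, the existing rule counts it correctly.

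This stands in part. It rules out two stronger readings that a reader might infer:
- That a worsening can never be counted. The documents do not support this, because a new entry would be counted.
- That it is missing from every AE table. The SAP list of tables was not available, and the protocol synopsis describes AE summaries without limiting them to TEAEs. The claim can be made only for the summaries described in protocol 12.3.5 and SAP 10.2.

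It does not remove the ambiguity. Two sites, or two monitors at one site, could follow the text and reach different classes for the same event.

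A second reply is that little is at stake. All AEs are listed, serious AEs reach the safety contact within 24 hours of awareness, and with eight subjects every event can be read individually. General status, current infection and non-permitted medication are re-checked on Day -1, which lowers the chance of an AE being open at dosing. This stands, and it limits the importance of the point.

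**Conclusion.** The point holds as a gap in definition and recording, with a probably small effect. As written, an AE with onset between consent and first inhalation that worsens or becomes serious afterwards is pre-treatment and only listed, unless the site chooses to enter the worsening separately. The documents do not clearly require that choice. Any resulting error lowers the TEAE counts.

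The size is 12.5 percentage points per affected subject in the overall row, and likewise in the drug-related or serious row where applicable. This assumes that all 8 planned subjects are dosed and that the site updates the existing record. A reader might want a probability that at least one of the eight subjects is affected. The documents give no rate from which to derive one, and any figure would rest wholly on the assumed risk, so none is offered here. Nothing suggests that a serious event would go unnoticed; what is at issue is the summary, not the reporting.

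**What to change.** 1. In protocol 12.3.5 and SAP 10.2, extend the TEAE definition: an AE with onset at or after the first inhalation, or an AE with earlier onset that increases in intensity or becomes serious at or after the first inhalation.
2. In protocol 7.1.2 and 10.8, or in the eCRF completion instructions, state that such a worsening is entered as a new AE with its own onset date and time. The programmed rule can then identify it; without a new entry or a recorded date of worsening, the wider definition could not be applied from onset dates alone.

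The cost is one sentence in each document and one recording instruction, with no new visits or assessments. The downside for the sponsor is that TEAE counts may become slightly less favourable.
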